## 2.3.6.1 Adverse effects

Adverse effects of using oral iron drugs include nausea, vomiting, abdominal pain, diarrhea, and constipation. Severity and incidence of such adverse effects depend on the amount of available ionized iron. GI toxicity is considered to be the consequence of direct mucous cells involvement [91].

Adverse effects associated with IPC use are, as a rule, minor and temporary. When using chewable IPC tablets or syrup, such GI symptoms as abdominal fullness, discomfort in upper abdominal cavity, dizziness, constipation, and diarrhea are rare [84].

A double-blind comparative study of 104 patients demonstrated that in the IPC group there were less adverse events, and there was a significant difference between patients receiving IPC or ferrous sulfate, as far as incidence of indigestion, nausea, and vomiting was concerned. Other adverse effects with 10% incidence noted in both therapeutic groups included abdominal pain, constipation, headache, and change of stool color [69].

In a multicenter comparative study of 113 patients (children) aged 6 to 48 months with iron deficiency anemia who received 2.5mg/kg of IPC for 90 days with or without food, only 3 patients of 113 had an adverse effect associated with iron therapy [70].

Monitoring of toxic adverse events showed that ferrous sulfate can cause gastric mucosa erosion or ulceration. This occurrence was not detected when using iron(III)-hydroxide polymaltose complex [68].

A randomized controlled study comparing toxicity and adverse effects range related to oxidizing action of ferrous sulfate and IPC in children with iron deficiency anemia showed only insignificant difference, however, SOD and LDL values were significantly higher in the IPC group [92].

Data of a comparative study with participation of 25 children with IDA who received IPC or ferrous sulfate showed that group there is a suppression of copper and ceruloplasmin metabolism in the ferrous sulfate group, whereas the IPC use did not influence the normal activity range of these processes [93].

A randomized study comparing bioavailability of iron(III)-hydroxide polymaltose and ferrous sulfate in blood donors with iron deficiency revealed such adverse effects as nausea and vomiting, which were less common in the IPC group. The difference was even more significant due to the fact that no donors in the IPC group interrupted the treatment on the grounds of adverse effects development [81].

As far as IPC tolerance is concerned, the drug is tolerated for long periods of time and is associated with insignificant minor adverse effects. This observation is especially important for iron therapy in the case of certain patients, such as pregnant women, children, and blood donors.

Effects causing treatment refusal

None.

Shifting from oral iron drugs

If a patient cannot take drugs orally, iron should be administrated intramuscularly or intravenously.

#### 2.3.6.2 Overdose

So far there have been no documented intoxication or excessive iron stock events in case of overdose, as iron of active substance iron(III)-hydroxide polymaltose complex is not present in the body in a free form and does not enter cells through passive diffusion [68].

Literature reflects specific issues of iron overdose in children. Most cases of death occur in childhood, especially in the age from 12 to 24 months. As little as 1-2 mg of iron can cause death, however, lethal cases are usually related to the intake of 2-10 mg. The incidence of iron intoxication is defined by its domestic availability, particularly if there are certain supplements left after pregnancy. Colorful sugar-containing coating of most commercially available tablets makes them look like candy. Therefore, all iron-containing drugs should be kept in child-proof bottles [94].

## 2.3.6.3 Local tolerance

Not applicable.

#### 2.3.6.4 Contraindications/Precautions

Ferrum Lek chewable tablets or syrup are contraindicated to patients with hypersensitivity to any of the drug components.

The drug is contraindicated to patients with excessive iron content or with disorders of iron utilization processes (hemosiderosis, hemochromatosis, lead anemia, sideroachrestic anemia, thalassemia), as well as with anemia not associated with iron deficiency.

The drug should not be prescribed to patients receiving repeated blood transfusion.

IPC should not be prescribed simultaneously with parenteral iron.

Precautions should be taken in patients with phenylketonuria (Ferrum Lek tablets contain aspartame, a source of phenylalanine in an amount equivalent to 1.5 mg/tablet).

Caution should be exercised in patients with diabetes mellitus. Insignificant increase in iron store concentration is associated with a significant increase in glucose homeostasis parameters [95].

Iron preparations are not used in patients with anemia caused by chronic inflammation or malignant neoplastic diseases, as iron is pooled in reticuloendothelial cells. Use of such iron to synthesize hemoglobin starts only after the elimination of pathology [96].

Oral iron drugs can color feces dark, but this effect is clinically insignificant.

There is data indicating that additional iron received by children without iron deficiency causes growth impairment [97].

If oral use of iron drugs was not successful, a possible reason could include incorrect diagnosis, a lack of compliance, constant bleeding, underlying infection, malignant neoplasms, liver disorders, and iron malabsorption.

#### 2.3.6.5 Usage during pregnancy and lactation

Animal studies of effects on reproduction identified no risk for offsprings. Controlled studies of pregnant women after the first pregnancy trimester showed no adverse reactions in mothers or the newborns. There is also no data on risk associated with this therapy during the first pregnancy trimester, negative influence on foetus is improbable [80].

Breast milk contains iron bound to lactoferrin. Only a small amount of iron from IPC complex is contained in breast milk; the likelihood of adverse effects in infants is very low. Toxic, cancerogenic, and mutagenic action of iron was not proven neither by means of clinical, nor epidemiological methods [80].

IPC tablets or syrup can be taken during pregnancy only after consultation with a physician.

#### 2.3.6.6 Paediatric use

Chewable tablets are not recommended for use in children under 3 years, as there's a risk of aspiration. Consequently, young children should receive IPC syrup.

In the case of children under 12 years, syrup is also a more preferable dosage form than chewable tablets, as it simplifies dose selection.

#### 2.3.6.7 Geriatric use

In the case of elderly patients with IDA, iron(III)-hydroxide polymaltose complex demonstrated high efficiency and good tolerance with minor adverse effects [83].

#### 2.3.6.8 Use in patients receiving dialysis

Multiple studies showed that oral iron therapy is inadequate when treating iron deficiency in patients on dialysis. In the case of such patients, intravenous iron administration is preferable [98].

#### 2.3.6.9 Influence on the ability to drive and use machines

No influence.

## 2.3.7 Post-marketing data

Apart from the well-known benefits of iron(III)-hydroxide polymaltose complex, there have lately been revealed other therapeutic advantages of such preparations.

Iron(III)-hydroxide polymaltose complex is a drug with slow release which enables only small amounts of iron to contact duodenal mucosa at a given period of time, increasing absorption and GI tolerance of the drug. Therefore, smaller amounts of iron provide the same therapeutic effect (compared to other iron drugs), and at the same time patient is ready to adhere to therapy recommendations thanks to the decreased amount of adverse effects. The drug demonstrates desired safety profile compared to other iron drugs and is suitable for treatment of patients with increased sensitivity to GI effects, namely pregnant women and children. It also more convenient to store at home, as far as children's safety is concerned, and can be for long periods of time and is associated with insignificant adverse effects. Such observations are also important for blood transfusion services, where administration of insignificant supplements helps to preserve adequate iron pool in the body, maintaining physical and psychological well-being of donors.

Iron in the form of various drug products is registered in many countries. Ferrum Lek is a iron(III)hydroxide polymaltose complex and has a long history of clinical use. Multiple post-marketing data of observational studies proves that iron(III)-hydroxide polymaltose complex has a favorable risk/benefit ratio and is one of the most efficient iron drugs [69, 70, 81, 82].

Despite the fact that the absorption of ferrous sulfate is more effective compared to other iron preparations, and daily increase of hemoglobin concentration is more prominent during first three weeks of therapy, iron(III)-hydroxide polymaltose complex provides equal efficiency in 9 weeks of treatment, whereas the volume of iron involvement into body processes is equal to that of ferrous sulfate.

Ferrum Lek is safe in coadministration with other drug products, which is not associated with the decrease of iron absorption. The drug is suitable for treatment of children, pregnant women, and elderly patients.

So far there have been no toxic reactions and overdose cases associated with iron(III)-hydroxide polymaltose complex.

Adverse events described in the SPC represent the range of possible adverse effects properly. Other issues related to the drug safety are described just as properly.

# **2.3.8** Conclusion of risks and benefits

All dosage forms of Ferrum Lek drug are indicated for treatment of iron deficiency manifestations in infants, children, adults, breastfeeding mothers, and pregnant women. Due to the fact that a low iron dose is recommended for treatment of latent iron deficiency in infants under 1 year, as well as iron deficiency prevention in infants under 1 year, children, adults, and breastfeeding mothers, tablets and syrup are not dosage forms traditionally used for such indications.

Iron(III)-hydroxide polymaltose complex is characterized by the same therapeutic action and safety profile as ferrous sulfate drugs. Conducted clinical studies were comprehensive and complied with the requirements of current clinical pharmacology. Not every study described in this review complied with the requirements of GCP. However, it does not affect the results of the review. Therapeutic efficacy of IPC seems to be appropriate to recommend this preparation as one of the most efficient preparation for additional iron therapy. Furthermore, IPC is a preparation of choice in case of high-risk categories of patients, such as preterm or newborn infants, children under eight years, and pregnant women, patients with ferrous sulfate intolerance. Cases of treatment refusal, interruption, and discontinuation are significantly less common in the case of IPC compared to other iron drugs.

Considering specific features and benefits, IPC drugs can be called a new generation of iron therapy.

Efficacy

Based on clinical use and well-controlled clinical studies, it was shown that IPC is a highly effective therapeutic drug for treatment of latent and manifesting iron deficiency forms, as well as the prevention of iron deficiency during pregnancy.

Described dosage forms have significant benefits, whereas the safety profile was improved, as iron of active substance in iron(III)-hydroxide polymaltose complex is not present in GI tract in a free form and does not get absorbed through passive diffusion.

It was proven that IPC has equal efficacy in iron-replacement therapy compared to ferrous sulfate, but it is much better tolerated.

#### Safety

Clinical studies demonstrated IPC safety in treatment of latent and manifesting iron deficiency forms, as well as the prevention of iron deficiency during pregnancy. Based on clinical use, there is a well-known range of adverse effects associated with the drug; these effects are predominantly minor and temporary. In general, chewable tablets and IPC syrup are well-tolerated.

Symptoms of GI tract irritation, such as abdominal fullness, pressure in epigastric region, nausea, constipation, and diarrhea, are very uncommon and present the most prevalent events. Dark stool color has no clinical significance. There were no registered toxic adverse effects or acute intoxication cases associated with the product.

Results of fecal occult blood test (hemoglobin selective) do not change when taking the drug, which makes it possible to continue treatment without interruption at the time of the test.

Ferrum Lek chewable tablets are contraindicated to patients with hypersensitivity to any of the drug components. The drug is contraindicated to patients with excessive iron content or with disorders of iron utilization processes (hemosiderosis, hemochromatosis, lead anemia, sideroachrestic anemia, thalassemia), as well as with anemia not associated with iron deficiency (hemolytic anemia).

Due to the low recommended iron dose chewable tablets are not used with children under 12 years. Chewable tables should not also be prescribed to children under 3 years, as there is a risk of aspiration, which means that these children should take syrup instead.

Precautions should be taken when prescribing Ferrum Lek to patients with diabetes mellitus or phenylketonuria.

Oral forms of iron therapy should not be prescribed to patients receiving EPO or dialysis for the correction of iron deficiency.

In the case of pregnancy or lactation, IPC tablets or syrup can be taken only after consultation with physician.

Toxic, cancerogenic, and mutagenic action of this drug was not proven neither by means of clinical, nor epidemiological tests.

Oral iron drugs should not be prescribed simultaneously with parenteral forms.

If oral use of iron drugs was not successful, a possible reason could include incorrect diagnosis, a lack of compliance, constant bleeding, underlying infection, malignant neoplasms, liver disorders, and iron malabsorption.

So far there has been no evidence of interaction with other drug products, so interaction with food components and accompanying drug products is unlikely.

Iron therapy should not be prescribed to patients receiving repeated blood transfusion.

The SPC submitted by the applicant adequately reflects indications for use, dose descriptions, and possible risks associated with the use of the product. Adverse effects are described together with observations made during clinical studies.

Latest data support the IPC use for treatment and prevention of iron deficiency in infants, children, and pregnant women.

# 2.4 Potential risk and benefit of the investigational drug products for the study participants

List of known adverse events associated with Ferrum Lek® (iron(III)-hydroxide polymaltosate) chewable tablets, 100 mg, manufactured by Lek d.d. (Slovenia) as compared with reference product Maltofer® (iron(III)-hydroxide polymaltosate), 100 mg chewable tablets (Vifor S.A., Switzerland) is present in Sections 2.1.1 and 2.1.2, respectively.

Clinical study will be conducted according to the protocol of the clinical study and the rules of Good Clinical Practice (decree of the Ministry of Health of the Russian Federation No. 200n dated 01.04.2016 "On Approval of Good Clinical Practice Rules", National standard of the Russian Federation GOST R 52379-2005 "Good Clinical Practice"), treatment of patients will be conducted by qualified healthcare personnel based on current clinical recommendations on treatment of patients with IDA. Treatment and examination during the study will be free of charge for the patients. Therefore, potential benefit of participating in the study exceeds potential risk of using the study and reference products.

# 2.5 Description and rationale for the route of administration, dosing regimens, and duration of treatment

The study drugs will be prescribed according to relevant Product Information:

Ferrum Lek® drug will be used according to the following scheme: 200 mg (2 tablets) with or immediately after meal to be taken as a single dose for 84 days.

Reference product Maltofer® will be used according to the following scheme: 200 mg (2 tablets) with or immediately after meal to be taken as a single dose for 84 days.

# **2.6 Description of the study population**

Adult patients of both sexes (18 years and older) with IDA and indication of iron therapy.

# **2.7** Legal framework for the conduction of clinical study

This is a protocol of the clinical study planned to be conducted in accordance with principles of the Declaration of Helsinki, World Medical Association (adopted at the 18th Assembly of the World Medical Association in Helsinki in June 1964, the latest revision adopted by the 64th Assembly in Fortaleza in October 2013), the triangular agreement on Good Clinical Practice (GCP, ICH E6(R2) dated 09.11.2016), and applicable laws of the Eurasian Economic Union and the Russian Federation:

- Rules for Registration and Expertise of Medicinal Products for Medical Use (adopted by Decision No. 78 of the Council of Eurasian Economic Commission dated November 3, 2016);
- Guideline for Good Clinical Practice of the Eurasian Economic Union (adopted by Decision No. 79 of the Council of Eurasian Economic Commission dated November 3, 2016);
- Federal Law No. 61-FZ "On Circulation of Medicines" dated 12.04.2010 (revision valid from January 1, 2017 with latest changes according to Federal Law No. 350-FZ dated July 3, 2016);
- Federal Law No. 152-FZ "On Personal Data" dated 27.07.2006 (revision valid from July 2017 with latest changes according to Federal Law No. 148-FZ dated 01.07.2017);
- Decree of the Ministry of Health of the Russian Federation No. 200n dated April 1, 2016 "On Approval of Rules for Good Clinical Practice";
- The national standard of the RF GOST R 52379-2005 "Good Clinical Practice".

- Government Decree of the Russian Federation No. 714 of September 13, 2010 (with latest changes and updates in revision dated October 15, 2014) "Rules for Compulsory Insurance of the Life and Health of a Patient Involved in Clinical Trials of a Drug";
- Order of the Ministry of Health of the Russian Federation On Approval of the Provision on the Ethics Council No. 986n dated November 29, 2012.

# **3** Study goals and objectives

# 3.1 Study purpose

The purpose of this study is to test the hypothesis of non-inferior efficacy and safety of Ferrum Lek® (iron (III) hydroxide polymaltosate), 100 mg chewable tablets (Lek d.d., Slovenia), as compared with MALTOFER® (Vifor S.A., Switzerland), in subjects with mild and moderate iron deficiency anemia.

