# **3.2. Study objectives**

# Main objective:

• To assess the non-inferiority of the therapeutic efficacy of Ferrum Lek® 2 tablets daily (200 mg), via assessing the effect on hemoglobin level in the blood (g/l) after 12 weeks of treatment for patients with iron-deficiency anemia of mild and moderate severity compared with MALTOFER® 2 tablets daily (200 mg) during the same period.

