## Secondary objectives:

• Assessment of safety of Ferrum Lek® 2 tablets daily (200 mg), compared with MALTOFER® 2 tablets daily (200 mg), via the frequency, characteristics, intensity and relationship to treatment received of AEs.

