# 4.2.5 Study type

Phase III multicenter randomized open-label prospective comparative parallel active-control study (in the Russian Federation). Randomization is a measure aimed at minimizing subjectivity due to random allocation of subjects. Randomization excludes subjective, as well as unperceived allocation of population, which differs significantly from the population of the second group, into one group by the Investigator.

A study of non-inferior efficacy and safety of Ferrum Lek® (iron-III-hydroxide polymaltosate), 100 mg chewable tablets (Lek d.d., Slovenia), compared to MALTOFER® (Vifor S.A., Switzerland), for treatment of mild and moderate iron deficiency anemia in adults, will be conducted.

#### Days Day 1 Day $29 \pm 2$ Day $57 \pm 2$ Day $84 \pm 2$ -7...-1 Day 98±2 Signing of ICF, screening Ferrum Lek® (n = 168)Treatment for 12 weeks Randomization n = 336MALTOFER® (n = 168)Follow-Up Visit No2 Visit 3 Visit 4 Visit 1 Visit 2 Visit 0

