#### 9.1.4 Safety parameteres analysis

Safety evaluation will include:

- 1) determination of the total number, incidence and severity of the folowing:
  - I. adverse events (AEs), regardless of their relationship to the treatment;
  - II. AEs associated or potentially associated with the drug;
  - III. AEs leading to discontinuation.

2) Gastrointestinal disorders (determined by means of a standardized MedDRA query for the corresponding symptoms), regarded by the Investigator as related to the study therapy, will be analyzed separately.

Methods of descriptive statistics will be used to represent the results. A comparison of the incidence of new AE cases in the study groups will be performed using the Fisher's exact test or

the chi-square test, depending on the number of proposed observations in one cell (<5 or  $\ge 5$ ), and a comparison of the severity (and the possible causality between the study drug and AE) will be conducted using the Cochran—Armitage test for linear trends for ordered categorical data.

3) Changes in the results of laboratory studies (conducted in the central laboratory) over time and the incidence of abnormal results of studies (based on the reference values of the central laboratory) will be summarized by group, and a comparison will be made between the groups using appropriate tests for quantitative and qualitative data (see below).

4) Changes in the vital signs over time and the incidence of pathological abnormalities revealed during physical examination will be summarized by group, and a comparison will be made between the groups using appropriate tests for quantitative and qualitative data (see below).

Comparison of quantitative data will be conducted using the t-test or the Mann—Whitney test, depending on the distribution normality (which will be estimated using the Shapiro—Wilk test).

Qualitative data will be compared using the exact Fisher's exact test or the chi-square test, depending on the number of proposed observations in one cell (<5 or  $\geq 5$ ).

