- 12) Non-inferiority margin is 5 g/L.
- 13) The significance level (two-sided, in accordance with FDA recommendations) is 95%, which corresponds to the type I one-sided error 0.05.
- 14) Power of the study is 80%, which corresponds to the type II error 0.20.
- 15) Statistical hypotheses evidence of a non-inferior efficacy:

- 16) The ratio between the study and control group sizes is 1:1
- 17) Interim analysis will be performed at 70% of the total sample size
- 18) O'Brien-Fleming alpha-spending function will be used with 80% power for efficacy boundary that will correspond to the following critical values for t-test: 2,628 for interim analysis (corresponds to p=0,005) and 1,976 for final analysis (corresponds to p=0,0245);

Calculation was performed using the clinfun package of Microsoft R Open software (available at https://mran.microsoft.com – Microsoft R Application network), that uses the group sequential design approach for the calculation of fixed sample sizes for the interim and final analysis. According to the output from the clinfun package, 143 subjects per group (286 subjects in total) should complete the study in order to confirm non-inferiority. 200 (100 per group) subjects should have evaluable data to perform interim analysis. Taking 15% withdrawal rate into account, one need to randomize 336 subjects (168 subjects per group). Taking 30% screening failure rate, up to 480 subjects should be screened to achieve target randomization.

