ITP	Iron transport proteins 1 and 2
RE	Reticuloendothelial (cells)
RES	Reticuloendothelial system
SBP	Systolic blood pressure
SAE	Serious adverse event
SOD	Superoxide dismutase
SOP	Standard operating procedure
TF	Transferrin
TfR	Transferrin receptor
FL	Federal law
Full name	First name, Patronymic, Last name
CNS	Central nervous system
Ср	Ceruloplasmin
RR	Respiration rate
HR	Heart rate
ECG	Electrocardiography

1. Introduction

This study is planned and carried out to demonstrate the non-inferiority and safety of Ferrum Lek[®] (iron (III) hydroxide polymaltosate), 100 mg chewable tablets (Lek d.d., Slovenia), compared to MALTOFER[®] (Vifor S.A., Switzerland), in subjects with mild and moderate iron deficiency anemia.

The objective of this Statistical Analysis Plan is more detailed, compared to Section 9 of the study protocol, description of the main principles of the protocol-based statistical analysis, description of the primary and secondary endpoints analysis methods as well as other data obtained during the study.

This Plan stipulates for conformance of the scheduled and conducted statistical analysis to the study protocol, including the definition of the analysis data sets, transformations and calculations for the endpoints, observations quantity needed, etc.

2. Study objectives and design

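### Protocol 3.1 and 4.2.5 word the non-inferiority hypothesis to include safety, which does not match the objectives, the only margin or the planned safety tests

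*Protocol*

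**What the plan says.** Two sentences attach non-inferiority to efficacy and safety together:

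- Protocol 3.1: "The purpose of this study is to test the hypothesis of non-inferior efficacy and safety", against the reference product.
- Protocol 4.2.5: "A study of non-inferior efficacy and safety of Ferrum Lek".

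The text that carries the objectives and the analysis is narrower:

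- Protocol 3.2, main objective: "To assess the non-inferiority of the therapeutic efficacy of Ferrum Lek", judged on haemoglobin after 12 weeks.
- Protocol 3.2, secondary objective: safety is assessed against the reference "via the frequency, characteristics, intensity and relationship to treatment received of AEs". Non-inferiority is not mentioned.
- SAP 1: "This study is planned and carried out to demonstrate the non-inferiority and safety of Ferrum Lek". SAP 2.1.1 and 2.1.2 make the same split as Protocol 3.2.
- Protocol 9.3: "Non-inferiority margin is 5 g/L". This is the only margin, and the only non-inferiority decision rule (Protocol 9.1.2, SAP 8.1) applies it to haemoglobin change.

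For safety, Protocol 9.1.4 says "A comparison of the incidence of new AE cases in the study groups will be performed using" Fisher's exact or chi-square test, and SAP 9.1 agrees. The protocol adds a Cochran-Armitage test for AE severity and causality, and t or Mann-Whitney tests for laboratory values and vital signs. Protocol 9.1 promises a 95% confidence interval for each proportion, but not for a difference between groups. The AE table layouts in SAP Appendix 1 give counts, percentages of AEs and a Fisher p-value.

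**The concern.** On its plain reading, Protocol 3.1 sets up a hypothesis about safety that nothing later in the plan can test. A non-inferiority conclusion needs a margin and an interval to set against it. A test of difference supplies neither, and its failure to reject shows only that the data did not separate the arms.

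At stake is what the final report may claim. If the purpose stays as worded, the only comparative result printed beside each AE row is a p-value. Nothing in either document stops a p-value above 0.05 from being offered as the answer to the safety half of the purpose. The early-stopping text (Protocol 9.2, SAP 11) adds to the looseness: the sponsor may stop if the study endpoints have been met, after an interim look at efficacy and safety, but what that means for AEs is not defined.

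**Working it through.** **1. What the trial is sized for.** Protocol 9.3 and SAP 2.3 give a margin of 5 g/L, SD 15 g/L, true difference 0, power 80% and a final critical value of 1.976. The formula is n per arm = 2·SD²·(z_α + z_β)² / margin².

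- Critical value 1.976: 2 × 225 × (1.976 + 0.842)² / 25 = 142.9, so 143, as stated.
- Dropout: 143 / 0.85 = 168.2, against 168 stated.

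The stated size reproduces from haemoglobin alone. No AE rate or safety margin enters it.

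**2. Inputs for safety.** The two-sided level is 0.05 (Protocol 9.4), with 168 patients randomised per arm. The documents state no overall AE rate. The 23% is the stool-discolouration figure in the product information (Protocol 2.1.1 and 2.1.2). The rates of 5%, 10%, 15% and 33% below are assumptions chosen to show a range. The patient is taken as the unit.

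**3. Precision.** The half-width of the 95% interval for a difference, with equal true rates p, is 1.96·√(2p(1−p)/168).

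| Rate p | Half-width |
|---|---|
| 5% | 1.96·√(0.0950/168) = 4.7 points |
| 10% | 1.96·√(0.1800/168) = 6.4 points |
| 23% | 1.96·√(0.3542/168) = 9.0 points |

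**4. Chance of a non-significant result when the test product is truly worse.** Power = Φ[(d − 1.96·s₀)/s₁]. Here d is the true difference, s₀ the standard error under the pooled rate and s₁ that under the two separate rates.

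- 10% vs 15%: s₀ = √(2 × 0.125 × 0.875/168) = 0.03608; s₁ = √((0.0900 + 0.1275)/168) = 0.03598. Power = Φ(−0.576) = 0.28, so p > 0.05 in about 72% of trials.
- 23% vs 33%: s₀ = √(2 × 0.28 × 0.72/168) = 0.04899; s₁ = √((0.1771 + 0.2211)/168) = 0.04869. Power = Φ(0.082) = 0.53, so p > 0.05 in about 47% of trials.

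Exact enumeration of the planned chi-square/Fisher rule gives 0.715 and 0.467. With 143 per arm it gives 0.752 and 0.528.

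**5. What a real safety non-inferiority test would need.** The margin here is hypothetical, since the documents give none. With one-sided 0.025, 80% power and equal rates, n per arm = (1.960 + 0.842)² × 2p(1−p) / margin².

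- 10-point margin at 10%: 7.849 × 0.18 / 0.01 = 141.3, so 142.
- 10-point margin at 23%: 7.849 × 0.3542 / 0.01 = 278.01, so 279.
- 5-point margin at 5%: 7.849 × 0.095 / 0.0025 = 298.3, so 299.

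With 168 per arm, such a test is adequately powered in some of these settings and not in others. The plan commits to none of them.

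**The case against.** The best defence is that this is loose wording in two sentences. The section straight after 3.1 confines non-inferiority to haemoglobin, the SAP repeats that split, and the title speaks only of evaluating efficacy and safety. The phrase can also be parsed as non-inferior efficacy, and separately safety, which is how SAP 1 reads. Safety results are to be presented descriptively. Protocol 9.1.4 already plans summaries of all AEs, related AEs and AEs leading to discontinuation, with related gastrointestinal disorders analysed separately. Low power for AE differences is normal in a trial sized on a laboratory endpoint, and the plan claims nothing else. Stool discolouration is called clinically unimportant in the product information, so a rise from 23% to 33% does not illustrate a clinically relevant harm.

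Most of this stands, and it limits the point to an inconsistency. The parsing defence is weaker for 3.1, which speaks of testing a hypothesis against the reference; on either reading no safety hypothesis is specified. The descriptive plan does not close the gap either, because the AE tables show percentages of events with a p-value and no patient-level risk or difference.

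A reader might infer that the sponsor intends to present a non-significant AE test as proof of non-inferior safety. The documents do not support that: no such rule is written. They simply do not exclude it.

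**Conclusion.** The inconsistency is real and minor. Protocol 3.1 and 4.2.5 promise more than Protocol 3.2, SAP 2.1 and the analysis sections provide. As planned, no safety result could establish non-inferior safety, and a non-significant AE test would be weak evidence for it: about 72% of trials would give one at 10% vs 15%, and about 47% at 23% vs 33%, with 168 per arm. Those figures depend on assumed rates (all but the 23%) and on a patient-level comparison.

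A reader might also conclude that the design is defective, or that a safety margin must be added. Neither follows. The objectives do not claim safety non-inferiority, so correcting the wording is enough, and the haemoglobin sample size is unaffected by this point.

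**What to change.** 1. Reword Protocol 3.1 and 4.2.5 to match 3.2: non-inferior efficacy, with safety described and compared.
2. In SAP 9.1 and the AE layouts of Appendix 1, report the number and percentage of patients with any AE, with a related AE and with a related gastrointestinal AE. For each, add the between-group risk difference and its 95% confidence interval.
3. State in SAP 9.1 that no safety non-inferiority conclusion will be drawn from a non-significant test.

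This needs no new data, visits or patients. It costs a wording change, one interval per summary row, and a slightly narrower claim.
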